7 TRIAL ASSESSMENTS

7.1 Assessments Related to Primary Endpoint

7.1.1 Number of Fertilized Oocytes

The number of fertilized oocytes will be assessed at 19±2 hours after insemination. Fertilized oocytes with 2 pronuclei will be regarded as correctly fertilized.

7.2 Assessments Related to Secondary Endpoints

7.2.1 βhCG Test

A blood serum β hCG test must be obtained 10-14 days after blastocyst transfer. If the test is positive according to the local laboratory's reference ranges, this confirms a positive β hCG. In case of doubtful / inconclusive β hCG result, a second test will be performed, preferably within 2 days, and the conclusive result recorded.

7.2.2 Clinical Pregnancy

Clinical pregnancy will be based on detection of at least 1 intrauterine gestational sac with fetal heart movement on transvaginal ultrasound at 5-6 weeks after blastocyst transfer. For clinical pregnancies, the number of intrauterine sacs and fetal heart beats will be recorded.

7.2.3 Ongoing Pregnancy

Ongoing pregnancy will be based on detection of at least 1 intrauterine viable fetus by transvaginal or abdominal ultrasound at 8-9 weeks after blastocyst transfer. For ongoing pregnancies, the number of intrauterine viable fetuses will be recorded.

7.2.4 Early Pregnancy Loss

Early pregnancy loss will be defined as a positive βhCG tests but no ongoing pregnancy at 8-9 weeks after blastocyst transfer, as described in sections 7.2.1 and 7.2.3 above.

7.2.5 Number and Size of Follicles during Stimulation

Transvaginal ultrasound will be performed at all visits during the stimulation period to count the number of follicles and measure the size of the follicles.

The total number of follicles and number of follicles with a diameter of ≤ 9 mm, 10-11 mm, 12-14 mm, 15-16 mm, and ≥ 17 mm on stimulation day 6 and last day of stimulation will be recorded. Data will be recorded separately for the right and left ovary.

Date: 14 Oct 2019 E-Study Protocol-21539; Ver. 6.0 Supersedes: 5.0 Page 59 of 103

7.2.6 Oocytes Retrieved

The number of oocytes retrieved will be recorded at the oocyte retrieval visit.

7.2.7 Metaphase II Oocytes

Maturity stage will be assessed prior to undergoing ICSI. Maturity stage will be categorized as germinal vesicle, metaphase I, metaphase II, degenerated or other.

7.2.8 Fertilization Rate

The number of pronuclei will be counted at 19±2 hours after insemination and recorded as 0, 1, 2 or >2. Fertilized oocytes with 2 pronuclei (2PN) will be regarded as correctly fertilized. Fertilization rate is the number of 2PN oocytes divided by the number of oocytes retrieved.

7.2.9 Number and Quality of Blastocysts on Day 5

The quality evaluation of blastocysts on day 5 after oocyte retrieval will consist of assessment of three parameters: blastocyst expansion and hatching status, blastocyst inner cell mass grading, and trophectoderm grading. The scoring is based on the classification system by Gardner & Schoolcraft¹², with the addition of D-categories for inner cell mass and trophectoderm.

Blastocyst expansion and hatching status will be assessed as 1 of the following:

- 1. An early blastocyst, blastocoel being less than half volume of that of the embryo.
- 2. A blastocyst with a blastocoel whose volume is half of, or greater than half of, that of the embryo.
- 3. A blastocyst with a blastocoel completely filling the embryo.
- 4. An expanded blastocyst with a blastocoel volume larger than that of the early embryo, with a thinning zona.
- 5. A hatching blastocyst with the trophectoderm starting to herniate through the zona.
- 6. A hatched blastocyst, in which the blastocyst has completely escaped from the zona.

For blastocysts with expansion and hatching status 3-6, blastocyst inner cell mass grading and trophectoderm grading will be evaluated.

Blastocyst inner cell mass grading will be assessed as 1 of the following:

- A. Tightly packed, many cells.
- B. Loosely grouped, several cells.
- C. Very few cells.

Supersedes: 5.0 Page 60 of 103

D. Degenerative or no inner cell mass.

Trophectoderm grading will be assessed as 1 of the following:

- A. Many cells forming a cohesive epithelium.
- B. Few cells forming a loose epithelium.
- C. Very few, large cells.
- D. Degenerative or very large cells.

Blastocysts with expansion and hatching status 3-6 will have a score combining the 3 parameters (blastocyst expansion and hatching status, inner cell mass, and trophectoderm); e.g., 4AB for a blastocyst with blastocyst expansion and hatching status 4, inner cell mass grading A, and trophectoderm grading B.

In the event of continued culture, blastocyst grading will not be recorded after day 5.

7.2.10 Endocrine Parameters during Treatment

During treatment, the following endocrine parameters will be evaluated: AMH, FSH, LH, hCG, E2 and P4.

Baseline assessments will be made for AMH, FSH, LH, hCG and P4 on stimulation day 1 and for E2 as part of confirmation of downregulation. Blood samples for FSH, LH, hCG, E2 and P4 will also be drawn on stimulation day 6 and on the last day of stimulation, and furthermore, FSH is also assessed at oocyte retrieval. Blood samples for AMH will also be drawn on the last day of stimulation, and at end-of-trial.

Analyses of AMH, FSH, hCG, LH, E2 and P4 will be performed at a central laboratory.

7.2.11 Serum FSH Concentrations

In addition to the sampling time points mentioned in section 7.2.10, blood samples will also be drawn on day 1 and at the oocyte retrieval visit for analysis of FSH.

Based on the serum FSH concentrations obtained during the trial, a population pharmacokinetic model will be developed. The modelling results will be reported separately.

7.2.12 Ovarian Hyperstimulation Syndrome

OHSS is defined as the total of early OHSS with onset ≤9 days after triggering of final follicular maturation, and late OHSS with onset >9 days after triggering of final follicular maturation. Classification of grade is based on Golan's classification system¹³ (see section 8.3 for details) and

Supersedes: 5.0 Page 61 of 103

all OHSS cases will be graded as mild, moderate or severe.

7.2.13 Adverse Events

Adverse events will be recorded from the time of signed informed consent for participation in the trial until the end-of-trial visit. For each adverse event the following parameters are recorded by the investigator on the Adverse Event Log: description of event, date and time of onset, intensity, causal relation to IMP, action taken to IMP, other actions taken, seriousness of the adverse event, date and time of outcome, and outcome. Definitions of adverse events are provided in section 8.

7.2.14 Injection Site Reactions

Every day throughout the stimulation period, the subjects will assess the local tolerability of subcutaneous injections of MENOPUR liquid or MENOPUR powder at three time points relative to the daily administration: immediately after the injection, 30 minutes after the injection and 24 hours after the injection. The subject will be informed to always inject MENOPUR liquid or Placebo to MENOPUR liquid using the pre-filled injection pen on the same side of the navel and MENOPUR powder or Placebo to MENOPUR powder using the syringe on the other side in order to be able to distinguish between injection site reactions related to MENOPUR liquid / Placebo to MENOPUR liquid and those related to MENOPUR powder / Placebo to MENOPUR powder. The following injection site reactions will be assessed: redness, pain, itching, swelling and bruising. The presence and intensity of each injection site reaction will be rated as one of the following: none, mild, moderate or severe.

The subject will record the assessments in a diary and the diary data will subsequently be transcribed to the e-CRF.

7.2.15 Anti-MENOPUR Antibodies

Blood samples for assessment of anti-MENOPUR antibodies in the individual subjects in the trial will be drawn pre-dosing and post-dosing:

- Screening [*Note*; this sample is exclusively used to re-establish the anti-drug antibody assays (e.g. screening- and confirmatory cut-points)]
- Stimulation day 1, prior to dosing (baseline; pre-dosing sample)
- 7-10 days after the last MENOPUR liquid or MENOPUR powder dose This may coincide with the transfer visit. Subjects not reaching transfer must be called in for this extra visit.
- 21-28 days after the last MENOPUR liquid or MENOPUR powder dose This may coincide with the βhCG visit. In case of discontinuation before the βhCG visit, this assessment should be done at the end-of-trial visit scheduled 21-28 days after the last

Supersedes: 5.0 Page 62 of 103

MENOPUR liquid or MENOPUR powder dose.

Ferring has developed the following assays for evaluating the immunogenicity of MENOPUR liquid or MENOPUR powder:

- Assay 1) A screening immunoassay, using labelled MENOPUR as capturing component, assessing the presence in serum of anti-MENOPUR antibodies, using a parametric cutpoint approach with a 5% false positive rate.
- Assay 2) A confirmatory immunoassay, using unlabeled MENOPUR for quenching of signal, confirming or disconfirming the specificity of any positive results in assay 1), using a parametric cut-point approach with a 1% false positive rate.
- Assay 3) A titer immunoassay determining the antibody response titer of any anti-MENOPUR antibodies confirmed in assay 2).
- Assay 4) A characterization step where any confirmed anti-MENOPUR antibodies will be tested for cross-reactivity towards FSH, hCG, LH and the structurally related TSH using the parametric cut-point with 1% false positive rate determined for assay 2).
- Assay 5) Neutralizing capacity of the antibodies confirmed positive in assay 2) and characterized for cross-reactivity in assay 4) will be assessed with three individual cell-based neutralizing antibody (NAb) assays (NAb FSH, NAb hCG and NAb LH) using a parametric cut-point approach with a 1% false positive rate. Samples that show cross-reactivity only to individual drug components (i.e. either to FSH, to hCG or to LH) will be tested only in the corresponding NAb assay. In case a confirmed positive sample show cross-reactivity to all drug components, it will be tested in all three NAb assays.

In subjects with a negative pre-dosing sample, a treatment-induced anti-MENOPUR antibody response will be defined as any post-dosing sample being positive in the confirmatory assay (i.e. assay 2).

In subjects with a positive pre-dosing sample, a treatment-induced anti-MENOPUR antibody response will be defined as a statistically determined fold increase in titers from the pre-dosing assessment to a post-dosing assessment.^a

A subject is defined to have treatment-induced anti-MENOPUR antibodies with neutralizing capacity, if the subject has any post-dosing sample being positive in assay 5) and the pre-dosing sample was negative in assay 5) [this also includes the scenario of pre-dosing sample negative in assays 1) or 2) and therefore not tested in assay 5)].

Ferring Pharmaceuticals

^a The fold increase in titres will be determined by minimum significant ratio (MSR) experiments during assay validation and will be stated in the validation report and the clinical trial report.

Supersedes: 5.0 Page 63 of 103

Subjects with a treatment-induced anti-MENOUPUR antibody response (both with and without neutralizing capacity) will be followed until the response becomes negative or has returned to predosing level. These subjects will be called in for assessments at 2 months after the last post-dosing anti-MENOPUR antibody sampling. If required, further assessments will be made at 3, 4, 6, 9 and 12 months after the last post-dosing anti-MENOPUR antibody sampling. The assessments will be terminated when two consecutive assessments are negative or indicate that the pre-dosing level has been reached, with a maximum follow-up period of one year. The assessments will also be terminated if the subject commences a new treatment cycle with any gonadotropin preparation.

7.3 Other Assessments

7.3.1 Demographics

Demographic information will be obtained during the screening period, including the following: date of birth, ethnicity (Hispanic or Latino, Not Hispanic or Latino) and race (American Indian or Alaska Native, Asian, Black or African American, Native Hawaiian or Other Pacific Islander, White).

7.3.2 Medical History

Any relevant medical history will be recorded during the screening period. This includes diagnosis / symptoms, and start and end dates (or marked ongoing in case it has not been resolved).

7.3.3 Menstrual History

Information about the menstrual history (average cycle length) will be obtained during the screening period.

7.3.4 Reproductive History

Information about the reproductive history will be obtained during the screening period. This will include number of clinical pregnancies, number of fetuses and outcome. Information on primary versus secondary infertility will be derived.

7.3.5 Infertility History

Information about the causes of infertility and duration of infertility will be obtained during the screening period. This will also cover information about any previous treatment for infertility, including type of treatment and gonadotropin preparations used.

Supersedes: 5.0 Page 64 of 103

7.3.6 Confirmation of Downregulation

Pituitary downregulation should be confirmed after minimum 10 days but no more than 20 days of GnRH agonist administration during the screening / downregulation period.

Downregulation is confirmed by a serum E2 level ≤20 pg/mL and transvaginal ultrasound showing no ovarian cysts.

7.3.7 Vital Signs

Systolic and diastolic blood pressure, pulse, and temperature will be measured at screening, on day 1, on the last day of stimulation and at end-of-trial. Assessments of blood pressure and heart rate are to be measured while the subject is seated after resting for 3 minutes. All blood pressure measurements should be made using the same arm and prior to any scheduled blood draws.

7.3.8 Physical Examinations

A complete physical examination will be performed at screening and end-of-trial. Information will be recorded for general appearance, central and peripheral nervous system, head and neck (including ears, eyes, nose, mouth and throat), respiratory system, cardiovascular system, gastrointestinal system, lymphatic system, urinary system, musculoskeletal system and skin.

In addition, height and weight, will be measured at screening for calculation of BMI, and body weight will be measured as part of the end-of-trial assessments.

At screening, each category will be evaluated as normal, abnormal not clinically significant or abnormal clinically significant. Abnormal clinically significant findings at screening must be reported on the Medical History Log.

At end-of-trial, potential changes from screening to end-of-trial will be evaluated for each category. In case of changes, these will be evaluated as normal, abnormal not clinically significant or abnormal clinically significant. Abnormal clinically significant changes from screening to end-of-trial must be recorded as adverse events.

7.3.9 **Gynecological Examinations**

A complete gynecological examination will be performed at screening and at end-of-trial. Information will be recorded for breast, external genitalia, vagina, cervix, uterus, ovaries and fallopian tubes.

Each category will be evaluated as normal, abnormal not clinically significant or abnormal clinically significant. Abnormal clinically significant findings at screening must be reported on the Medical History Log.

Supersedes: 5.0 Page 65 of 103

7.3.10 Clinical Laboratory Variables

Central Laboratory Tests

The following laboratory tests will be performed by a central laboratory:

- Screening, last day of stimulation and end-of-trial visit: serum chemistry: non-fasting glucose, blood urea nitrogen, creatinine, potassium, sodium, chloride, calcium, aspartate aminotransferase, alanine aminotransferase, and gamma-glutamyl transferase.
- Screening, last day of stimulation and end-of-trial visit: hematology: red blood cell count, white blood cell count, hematocrit, hemoglobin, platelet count, and differential count.
- Screening, day 1, last day of stimulation and end-of-trial visit: AMH. An AMH level greater than 1.0 ng/mL should be documented at screening.
- Downregulation, day 6, and last day of stimulation: E2. An E2 level of ≤20 pg/mL should be documented to confirm downregulation prior to randomization.
- Day 1, day 6, last day of stimulation and oocyte retrieval: FSH.
- Day 1, day 6, and last day of stimulation: hCG, LH and P4.

The samples for AMH, FSH, LH, hCG and P4 on stimulation day 1 (baseline) will be collected prior to the first dose of MENOPUR liquid or MENOPUR powder. For E2, the sample confirming downregulation will be used as baseline. Samples drawn on stimulation day 6 and on the last day of stimulation will be collected at least 8 hours after the previous MENOPUR liquid, MENOPUR powder or GnRH agonist administration.

The investigator will review the laboratory results and evaluate and document whether the results are normal or abnormal and whether or not abnormal results are clinically significant. The laboratory report will be signed and dated by the investigator.

Local Laboratory Tests

The following laboratory tests prior to randomization will be performed at each site's local or reference laboratory per standard practice if results are not already available in the subject's chart. Furthermore, analysis of hormones after randomization may also be performed locally. Results will be reviewed by the investigator and documented in the subject's chart and e-CRF (if applicable).

 Hormones prior to randomization: total testosterone, prolactin, and TSH should be drawn at screening or within 12 months prior to screening and documented to be within normal limits or considered not clinically significant by the investigator. In addition, the early follicular phase (cycle day 2-4) serum FSH level should be between 1-12 IU/L within 3 months prior to randomization. Trial Code: 000303 Date: 14 Oct 2019 E-Study Protocol-21539; Ver. 6.0 Supersedes: 5.0

Page 66 of 103

- Other laboratory assessments prior to randomization: serum hepatitis B surface antigen, hepatitis C antibody, HIV antibody, and rapid plasma reagin tests are to be done at screening, if not done within 6 months prior to screening, and documented to be negative.
- Hormones after randomization: E2 and P4 may be analyzed at various time points during stimulation (optional), and serum βhCG is to be analyzed for pregnancy monitoring.

7.3.11 Blastocyst Transfer Procedure

Any difficulty or eventuality during the transfer procedure will be noted.

7.3.12 Malfunction of Pen

In case of technical malfunction of a pen, that results in a replacement of the pen, all relevant details (including time, date, a description of the malfunction and whether dosing was affected) of the incidence should be reported in a blinded manner in the e-CRF, the pen should be replaced and the treatment continued. Human errors such as misunderstanding of instructions or incorrect handling of the pen should not be regarded as technical malfunctions.

In case of adverse events caused by malfunction of the pen, these will be identified and described.

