2.2 Endpoints

Primary Endpoint

• Number of fertilized (2 pronuclei [2PN]) oocytes at 19±2 hours after insemination.

Secondary Endpoints

- Positive βhCG rate (positive βhCG test 10-14 days after blastocyst transfer).
- Clinical pregnancy rate (transvaginal ultrasound showing at least 1 intrauterine gestational sac with fetal heart beat 5-6 weeks after blastocyst transfer).
- Ongoing pregnancy rate (at least one intrauterine viable fetus 8-9 weeks after blastocyst transfer).
- Early pregnancy loss (defined as a positive βhCG test but no ongoing pregnancy at 8-9 weeks after blastocyst transfer).
- Follicular development as assessed by transvaginal ultrasound on stimulation day 6 and last day of stimulation.

- Endocrine profile:
 - Serum follicle-stimulating hormone (FSH) on day 6, last day of stimulation and at oocyte retrieval, and corresponding population pharmacokinetics (PK) analysis.
 - Serum Anti-Müllerian hormone (AMH) on last day of stimulation and at end-of-trial.
 - Human chorionic gonadotropin (hCG) and luteinizing hormone (LH) on day 6 and last day of stimulation.
 - Estradiol (E2) and progesterone (P4) on day 6 and last day of stimulation.
- Number of oocytes retrieved, number of metaphase II oocytes, fertilization rate, and number and quality of blastocysts 5 days after oocyte retrieval.
- Total gonadotropin dose and number of stimulation days.
- Frequency of OHSS (early OHSS if the onset is ≤9 days after triggering of final follicular maturation and late OHSS if the onset is >9 days after triggering of final follicular maturation).
- Frequency and intensity of adverse events.
- Changes in circulating levels of clinical chemistry and hematology parameters and proportion of subjects with markedly abnormal changes.
- Frequency and intensity of injection site reactions (redness, pain, itching, swelling and bruising) assessed by the subject during the stimulation period.
- Frequency of treatment-induced anti-MENOPUR antibodies, overall as well as with neutralizing capacity.
- Technical malfunctions of the pen.

Post-trial Endpoints

- Live birth rate.
- Late pregnancy loss rate (defined as an ongoing pregnancy but no live birth).
- Neonatal health including SAEs at birth, and SAEs at 4 weeks and minimum 6 months after birth.

Date: 14 Oct 2019 E-Study Protocol-21539; Ver. 6.0 Supersedes: 5.0

[figure not shown]
Page 26 of 103

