9.8.6 Technical Malfunctions of the Pen

Technical malfunctions of the pen is a secondary endpoint. The frequency of technical malfunctions of the pen will be tabulated.

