10.2.6 Technical Malfunction of the Pen

The frequency of reported malfunctions of the administration pen will be presented in a summary table.

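### Only pen malfunctions that lead to replacement have to be reported, while the endpoint and its tables cover all technical malfunctions, so the tabulated rate can only err on the low side

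*Protocol*

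**What the plan says.** The protocol lists "Technical malfunctions of the pen" as a secondary endpoint in section 2.2, with no qualifier. The synopsis and SAP 2.2 do the same.

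The only collection instruction is Protocol 7.3.12. It begins "In case of technical malfunction of a pen, that results in a replacement of the pen, all relevant details" and goes on to ask for the time, the date, a description and whether dosing was affected. It then says that "the pen should be replaced and the treatment continued". A separate sentence narrows the definition: "Human errors such as misunderstanding of instructions or incorrect handling of the pen should not be regarded as technical malfunctions". Another deals with safety consequences: "In case of adverse events caused by malfunction of the pen, these will be identified and described".

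On analysis, Protocol 9.8.6 states: "The frequency of technical malfunctions of the pen will be tabulated". SAP 10.2.6 states: "The frequency of reported malfunctions of the administration pen will be presented in a summary table". Neither section mentions replacement, and neither gives a denominator.

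**The concern.** Replacement is one possible consequence of a fault; it does not define a fault. A pen can jam, leak or deliver short without being exchanged, for instance when the problem appears as the pen is finished or when the subject gets round it. Section 7.3.12 shows an interest in whether dosing was affected, yet a fault that affected dosing without replacement falls outside its reporting trigger.

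At stake is the meaning of one descriptive rate. The drug substance is the same in both formulations and the pen is what is new, offered for convenience (Protocol 1.1 and 1.2). A reader will take the table as the frequency of all technical malfunctions. If sites follow 7.3.12 as written, it is the frequency of malfunctions that ended in replacement.

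**Working it through.** The plan gives no expected malfunction rate, target or precision, so there is no figure to reproduce. The check is mainly a comparison of texts.

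**1. Scope at each step**

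| Step | Place | Limited to replacement? |
|---|---|---|
| Endpoint | Protocol synopsis and 2.2; SAP 2.2 | No |
| Collection | Protocol 7.3.12 | Yes, and human error excluded |
| Protocol analysis | Protocol 9.8.6 | No |
| SAP analysis | SAP 10.2.6 | No, but counts what was reported |

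The SAP table covers "The frequency of reported malfunctions of the administration pen", so it inherits the collection filter without saying so.

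**2. Other routes by which an unreplaced fault could surface**

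- Protocol 5.6: used and unused pens come back at each visit and discrepancies are discussed. Nothing links this to the endpoint.
- Protocol 8.5.2: overdoses and medication errors are tracked in the e-CRF for pharmacovigilance review. There is no link to the endpoint.
- Protocol 9.7 and SAP 8.1.3: subjects who deviate from planned treatment are listed. There is no link to the endpoint.
- Protocol 7.3.12: adverse events caused by a malfunction are described. This does not cover faults without an adverse event.
- Protocol 6.2.1 and 7.2.14: the home diary is specified for injection site reactions only, although subjects inject at home.

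Some faults may be visible in these records, but no instruction carries them into the device table.

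**3. Direction**

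If *m* is the share of true malfunctions that go unreported under the rule, then expected recorded = N × p × (1 − m), with m ≥ 0. The recorded figure cannot exceed the true one through this mechanism.

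For scale, take the 400 planned subjects, all of whom use an active or placebo pen. Assume p = 2% and m = 10% to 30%; neither value is in the documents.

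- True: 400 × 0.02 = 8
- Recorded at m = 10%: 8 × 0.90 = 7.2
- Recorded at m = 30%: 8 × 0.70 = 5.6

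**4. How often the opportunity arises**

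A pen holds 1200 IU and the starting dose is 225 IU. Since 1200 / 225 = 5.33, a pen gives five full doses (1125 IU) and leaves 75 IU. Count the dosing days that are a pen's last use or the last stimulation day, with the dose held at 225 IU and the durations assumed:

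- 7 days: 2/7 = 29%
- 9 days: 2/9 = 22%
- 10 days: 2/10 = 20%
- 12 days: 3/12 = 25%
- 20 days: 4/20 = 20%

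Holding the dose after day 5 anywhere from 75 to 450 IU, over 7 to 20 days, gives 10% to 35% if a dose may be split across two pens and 10% to 45% if not. The upper ends put the dose at 450 IU from day 6, which the 75 IU adjustment steps would not allow, so they are outer limits.

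These shares count days on which replacement is less likely. They do not estimate *m*: a fault on such a day may still lead to replacement, and a fault worked around on any other day is not included.

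**The case against.** The best defence is that the sentence in 7.3.12 presumes replacement. It tells sites to replace the pen, so its authors may have regarded replacement as part of any true malfunction. Nothing forbids reporting other faults, and neither analysis section would filter them out. The e-CRF page and the handling guideline cited in Protocol 5.4 are not available and might ask for more. Replacement is also an objective threshold that helps separate device faults from mishandling. Both arms use pens of identical appearance under one rule, and no between-arm test of malfunctions is planned.

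Part of this stands. The accurate statement is that unreplaced faults are not required to be captured; it would go too far to say that they are lost. The presumption still fails for a fault found when that pen has no further dose to give, and for one the subject overcomes. The threshold is not needed to screen out mishandling, because the human-error sentence does that separately.

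Three stronger readings are tempting and not supported:

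- **An undercount of about 20% to 30%.** This would add one dose in five from the first pen to one day in ten of an assumed 10-day stimulation. The denominators differ; on those same assumptions the count is 2 of 10 days. It also assumes that no fault on those days leads to replacement. A pen failing on its fifth dose leaves that dose undelivered, which is a reason to replace it. The end of stimulation is decided at a visit (Protocol 6.2.4), so a subject taking her last home dose need not know that it is the last.
- **Under-delivery in the liquid arm would go unexplained.** The accountability, medication-error and non-compliance records could reveal it.
- **Nothing else in the trial bears on how the pen performs.** That is true only of mechanical faults. Total dose, serum FSH and injection site reactions also bear on delivery.

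**Conclusion.** The concern holds as a mismatch between what is collected and what the endpoint claims. Sites that follow 7.3.12 exactly will produce a malfunction rate that is, if anything, too low, and the loss falls mainly on faults without an adverse event. The size cannot be derived from the documents; the day shares and the 8 versus 5.6 to 7.2 illustration rest on assumed rates, durations and doses.

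The consequence is confined to a descriptive secondary endpoint. The primary analysis, sample size and type I error are untouched. The conclusion rests on 7.3.12 being the only collection instruction; an e-CRF page that already asks for every fault would reduce the point to a wording correction. It is still worth correcting, because the pen is the new presentation and the remedy is small.

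**What to change.** - **Protocol 7.3.12:** delete the clause that makes replacement a condition for reporting. Keep the human-error exclusion. The instruction on replacing the pen should keep its present scope; only the reporting trigger changes. For each report, record pen replaced (yes/no) and dose affected (yes/no); the second puts into fixed form something the section already asks for.
- **SAP 10.2.6:** tabulate any malfunction, malfunction with replacement and malfunction with dose affected, by pen content (active or placebo) and overall. State the denominator, for example pens dispensed or subjects treated.
- **If collection can no longer change:** label the table as malfunctions resulting in pen replacement, and say that other faults were not required to be reported. This may be the practical option, since SAP version 2.0 is dated 17 Aug 2021 and the protocol planned the last subject's last visit for Q4 2020, although recruitment was paused in between.

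The cost is two tick boxes, one fuller table, a few more site reports and a somewhat higher malfunction rate. Relabelling costs nothing but leaves the missing faults uncounted.
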